3.8.3.4 Withdrawal of Consent

All subjects have the right to withdraw their consent from further participation in the trial at any time without prejudice. Subjects cannot withdraw consent for use of data already collected as part of the trial, but only for future participation. The investigator can also discontinue a subject's participation in the trial at any time if medically necessary. Unless the subject provides their written withdrawal of consent or there is other written documentation by the investigator confirming the subject's verbal intent to completely withdraw from the trial, subjects should be followed for all protocol-specified evaluations and assessments, if possible.

Complete withdrawal of consent requires a subject's refusal of ALL of the following methods of follow-up (these methods of follow-up will also be noted in the trial ICF):

- Participation in all follow-up procedures specified in the protocol (whether in-clinic, by telephone, or by an in-home visit).
- Participation in a subset of protocol specified follow-up procedures (by a frequency schedule and method, as agreed by subject and staff).
- Contact of the subject by trial personnel, even if only by telephone, to assess current medical condition, and obtain necessary medical or laboratory reports relevant to the trial's objectives.
- Contact of alternative person(s) who have been designated in source records as being available to discuss the subject's medical condition, even if only by telephone, mail, or e-mail (eg, family, spouse, partner, legal representative, friend, neighbor, or physician).
- Access to medical information from alternative sources (eg, hospital/clinic medical records, referring doctor's notes, public records, dialysis, transplantation or vital registries, social media sources).

Protocol 341-201-00004

Withdrawal of consent is a critical trial event and therefore should be approached with the same degree of importance and care as is used in initially obtaining informed consent. The reasons for a subject's intended withdrawal need to be completely understood, documented, and managed to protect the rights of the subject and the integrity of the trial. A subject may initially express their desire to discontinue IMP administration, which is not equivalent to a complete withdrawal of consent for further participation (see [Section 3.8.3.2](#)). A subject may, however, indicate that further trial participation is creating a burden on their work or social schedule. Therefore, the investigator should follow the procedures outlined in [Section 3.8.3.3](#) to determine if the subject can continue participation in the trial if modifications to his/her treatment and/or schedule of assessments can be accommodated. Only subjects who withdraw their permission for all of the above degrees of follow-up are considered to have completely withdrawn their consent to participate in the trial.

Subjects who withdraw from the trial will not be replaced.

3.8.3.5 Continued Trial Participation After IMP Discontinuation

In all cases of impending IMP discontinuation or consent withdrawal, investigators will be given instructions to meet and discuss with the subject their options of continuing in the trial. The investigator should ensure understanding and documentation of the reasons for the subject's desire to withdraw consent. Subjects who discontinue IMP are allowed to stay in the trial and have efficacy evaluations at Week 12. Subjects who achieve clinical remission during the trial should be encouraged to stay in the trial, have their efficacy evaluation at Week 12, and see if they can achieve endoscopic remission in addition to clinical remission.

3.9 Screen Failures

A screen failure subject is one from whom informed consent is obtained and is documented (ie, subject signs an ICF), but who is not randomized or assigned to trial treatment. Subjects who sign an ICF but who are not started on treatment are permitted to be rescreened. Subjects excluded for drug or alcohol abuse are not eligible to be rescreened for participation in the trial. However, subjects excluded for other reasons may be rescreened at any time if the exclusion characteristic has changed. Subjects are permitted to be rescreened 3 times. In the event that the subject is rescreened, a new ICF must be signed, a new screening number assigned, and all screening procedures repeated.

Protocol 341-201-00004

3.10 Definition of Completed Subjects

The treatment period is defined as the time period during which subjects are evaluated for primary and/or secondary objectives of the trial irrespective of whether or not the subject actually consumed all doses of the IMP. Subjects who are evaluated at the last scheduled visit during the treatment period will be defined as trial completers. Subjects who complete the Week 12 visit on IMP will be considered as on-treatment completers. Subjects who discontinue IMP but complete the Week 12 visit will be considered as off-treatment completers.

3.11 Definition of Subjects Lost to Follow-up

Subjects who cannot be contacted on or before the 30-day post-treatment follow-up, who do not have a known reason for discontinuation (eg, withdrew consent or AE), and for whom a survival status at the end of the trial cannot be determined will be classified as “lost to follow-up” as the reason for discontinuation. Survival status can be determined from a variety of sources, either by obtaining acceptable documentation for death (ie, death certificate, medical records, public records, statement by a family member or primary care physician) or acceptable documentation for life (ie, direct contact with the subject, medical records, successful telephone contact with the subject, statement by a family member or primary care physician, or public records).

The site will make 3 documented attempts to contact the subject by telephone and in the event the site is unable to reach the subject by telephone, the site will attempt to contact the subject via certified mail or an alternative similar method, where appropriate, before assigning a “lost to follow-up” status.

3.12 Subject Compliance

The date and time of the first dose of IMP administration will be recorded. The date and time of the dose administered on the days of blood sampling for PK analysis will also be recorded. Information regarding any missed or inappropriately administered doses will also be documented in eSource. Subjects with > 20% missed doses will be considered noncompliant. If subjects do not comply with the protocol, it is at the discretion of the investigator and sponsor to terminate their participation in the trial.

Protocol 341-201-00004

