3.8.3 Individual Subject Discontinuation

3.8.3.1 Treatment Interruption

All attempts should be made to avoid treatment interruption during the trial. For subjects who have an interruption of treatment, the investigator or designee will contact the sponsor at the earliest possible time by telephone. The sponsor should be notified when there is a planned or inadvertent treatment interruption of 4 days or more in a 7-day period. The investigator and sponsor will come as quickly as possible to a joint decision regarding the subject's continuation in the trial. This decision will be documented by the investigator and the sponsor, and reviewed by the trial site monitor. The treatment interruption will be recorded in eSource and also recorded as a protocol deviation (Section 3.13).

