3.13 Protocol Deviations

In the event of a significant deviation from the protocol due to an emergency, accident, or mistake (eg, violation of informed consent process, IMP dispensing or subject dosing error, treatment assignment error, subject enrolled in violation of eligibility criteria or concomitant medication criteria), the investigator or designee will contact the sponsor at the earliest possible time by telephone. The investigator and sponsor will discuss the details of the deviation and agree upon the subject's continuation in the trial. This decision will be documented by the investigator and the sponsor, and reviewed by the site monitor.

4 Restrictions

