7.4.1 Primary Endpoint Analysis

The primary endpoint of the trial is the percentage of subjects who, at Week 12, achieve clinical remission (CDAI score < 150).

Protocol 341-201-00004

Logistic regression with terms of treatment group, the randomization stratification factors, location of disease, country, age, sex, disease duration, smoking habit, and baseline CDAI, and baseline CDAI with CDAI stratification factor interactions will be applied to the primary endpoint. The efficacy sample will be used in the efficacy analysis. Remission and nonremission subjects (ie, treatment failures) are defined as follows:

- Subjects who complete the trial and meet the primary endpoint definition at Week 12 without increasing dosages of baseline Crohn's disease medications or taking a new medication for Crohn's disease during the double-blind treatment period will be considered as remission subjects for the endpoint.
- Subjects who increase dosages of baseline Crohn's disease medications or take a new medication for Crohn's disease during the double-blind treatment period, or subjects who withdraw from the trial during the double-blind period, in addition to the subjects who fail to meet the primary endpoint at Week 12, will be considered as nonremission subjects for the endpoint.

The primary analysis of this trial is comparison of the pooled OPS-2071 600 mg BID and 300 mg BID treatment groups with placebo in the primary endpoint of clinical remission. If this analysis is significant at a 2-sided alpha level of 0.05, comparisons to OPS-2071 600 mg BID versus placebo and OPS-2071 300 mg BID versus placebo in the primary endpoint will be conducted with a 2-sided alpha level of 0.05 in each comparison. If the comparison of the pooled OPS-2071 dose groups versus placebo in the primary endpoint is significant at a 2-sided alpha level of 0.05, and a comparison, say, OPS-2071 600 mg BID versus placebo, is also significant at a 2-sided alpha level of 0.05, the null hypothesis of equal response of OPS-2071 600 mg BID and placebo in the primary endpoint will be considered rejected with an experiment-wise Type I error of 0.05.

The comparison between OPS-2071 150 mg BID versus placebo in the primary endpoint is considered as a secondary analysis and is provided in [Section 7.4.2](#).

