Subjects who increase dosages of baseline Crohn's disease medications or take a new therapy for Crohn's disease during the trial and subjects who withdraw from the trial early are considered as treatment failures in the ITT analysis of all of the primary and secondary response/remission endpoints. Subjects who discontinue IMP during the trial with no baseline Crohn's disease medication dosage increases and/or new therapy for Crohn's disease through Week 12 are encouraged to stay in the trial and take primary and secondary endpoint evaluations at Week 12 for efficacy analyses. Hence, missing data at Week 12 due to subjects' early withdrawal is handled by an ITT analysis with all subjects who early withdraw from the trial treated as treatment failures.

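### Noncompliance or a dosing interruption can end trial participation, with no stated criterion, and so force a nonremission score, while subjects who stop IMP altogether may stay and be scored on their Week 12 CDAI

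*Protocol*

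**What the plan says.** **Routes to removal.** Protocol 3.12 first sets a label: "Subjects with > 20% missed doses will be considered noncompliant". It then adds: "If subjects do not comply with the protocol, it is at the discretion of the investigator and sponsor to terminate their participation in the trial". What may be ended is participation in the trial, not only dosing. Section 3.8.3.1, on treatment interruption, says: "The investigator and sponsor will come as quickly as possible to a joint decision regarding the subject's continuation in the trial". Section 3.13 has a parallel sentence for significant deviations: "The investigator and sponsor will discuss the details of the deviation and agree upon the subject's continuation in the trial". None of the three sections states a criterion for the decision.

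**Scoring after removal.** Protocol 7.4.1 reserves remission for "Subjects who complete the trial and meet the primary endpoint definition at Week 12" who have had no increase in, or addition to, their Crohn's medication. Those who withdraw in the double-blind period are nonremission. SAP 8.1.3 repeats this, and SAP 8.1.1 has "all subjects who early withdraw from the trial treated as treatment failures". The analysis set named in Protocol 7.4.1 and SAP 8.1.2 is the Efficacy Sample/FAS, which requires a postbaseline CDAI (Protocol 7.2, SAP 5.1). Table 3.7-1 schedules the first of these at Week 2.

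**Retention after stopping IMP.** Section 3.8.3.5 says: "Subjects who discontinue IMP are allowed to stay in the trial and have efficacy evaluations at Week 12". Section 3.8.3.2 agrees for subjects on stable baseline Crohn's medication, 7.3.1 encourages it, and 3.10 has a category for completers who are off treatment. Section 3.8.3.4 makes follow-up the default, where possible, unless complete withdrawal of consent is documented.

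**The concern.** Two policies sit side by side. One keeps subjects who have stopped the drug and uses what happened to them at Week 12. The other allows subjects who take the drug imperfectly to be dropped, after which their Week 12 status cannot count. As written, a subject who took 75% of doses could be removed and scored a failure, while a subject who stopped at Week 2 could stay and be scored a remission. The plan gives no reason for the difference.

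Adherence is observed after randomisation and may depend on tolerability, and so on dose. A removal on these grounds replaces an outcome that could have been observed with an imposed failure. It is avoidable, because the protocol already provides for following such subjects. The sample-size section states no dropout allowance, and section 3.3.1 says withdrawn subjects are not replaced.

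**Working it through.** **1. The rules compared**

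| Subject | May stay to Week 12? | Primary outcome |
|---|---|---|
| Stops IMP, no Crohn's medication increase or addition | Yes (3.8.3.2, 3.8.3.5, 7.3.1) | Actual Week 12 CDAI |
| Misses doses or interrupts, kept in trial | Yes | Actual Week 12 CDAI |
| Misses doses or interrupts, removed after a postbaseline CDAI | No (3.12, 3.8.3.1) | Nonremission |
| Same, removed before any postbaseline CDAI | No | Outside the FAS |

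The last three rows can describe the same adherence record. What separates them is the decision to remove and its timing.

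**2. The plan's own power.** Inputs from Protocol 7.1: 40% versus 20%, 60 per group, 2-sided alpha 0.05. The primary comparison pools 600 mg and 300 mg, so it is 120 versus 60. The pooled-variance normal approximation is

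power = Φ[(d − 1.96·SE0)/SE1], with SE0 = √(p̄(1−p̄)(1/60+1/120)) and SE1 = √(pP(1−pP)/60 + pA(1−pA)/120).

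- p̄ = (60×0.20 + 120×0.40)/180 = 0.333
- SE0 = √(0.2222×0.025) = 0.0745
- SE1 = √(0.00267 + 0.00200) = 0.0683
- power = Φ[(0.200 − 0.1461)/0.0683] = Φ(0.789) = 78.5%

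The plan states 80%; exact enumeration of the uncorrected chi-square test gives 79.2%. The single-dose figure computes to 67.0%, against 67% stated. There is no arithmetic error here. These are unadjusted calculations, whereas the planned model is covariate-adjusted.

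**3. Effect of removals (illustration).** The documents give no removal rate, so the shares below are assumptions. I also assume that removed subjects have a postbaseline CDAI and would have remitted at their arm's planned rate. The scored rate is then the planned rate × (1 − share removed).

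| Removed, active / placebo | Scored rates | Difference (points) | Power |
|---|---|---|---|
| 0% / 0% | 40% vs 20% | 20 | 78.5% |
| 2% / 2% | 39.2% vs 19.6% | 19.6 | 77.2% |
| 5% / 5% | 38% vs 19% | 19 | 75.2% |
| 10% / 10% | 36% vs 18% | 18 | 71.7% |
| 10% / 5% | 36% vs 19% | 17 | 66.0% |
| 10% / 0% | 36% vs 20% | 16 | 60.0% |
| 0% / 10% | 40% vs 18% | 22 | 86.8% |

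**4. One subject.** Converting one would-be remission to a failure moves the pooled active rate by 1/120 = 0.83 points and the placebo rate by 1/60 = 1.7 points.

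**5. Type I error.** With a true rate of 20% in both arms, equal removal of 5% or 10% leaves the exact chi-square error at about 0.050. Removing 10% from one arm only gives about 0.066 (active) or 0.059 (placebo).

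**The case against.** The other side has real force, and it limits the point in several ways.

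- **A reader might infer that the discretion sets the primary outcome.** It does not. A retained subject must still reach CDAI below 150 without a medication increase or addition. The decision works in one direction only.
- **A reader might infer that missing more than 20% of doses triggers removal.** Section 3.12 does not say so. That sentence only assigns a label; the next is permissive and concerns noncompliance with the protocol generally. The 75%-of-doses contrast is possible under the text, not prescribed by it.
- **A reader might infer that an arm could be favoured deliberately.** Section 3.6 blinds the investigator, and sponsor staff in monitoring, data management and analysis have no access to the codes. The sponsor shares in each decision, which tempers variation between about 100 sites, and 3.8.3.1 requires documentation and monitor review. Bias therefore needs adherence or removal to differ by arm for another reason. Section 1.3 reports no withdrawal due to an adverse event related to OPS-2071, although multiple dosing in those trials lasted at most 10 days, against 12 weeks here.
- **There is a sensitivity analysis.** The placebo-based imputation (Protocol 7.4.1.1, SAP 8.1.4.1) covers subjects who withdraw before Week 12. It tests the failure scoring in part, but cannot restore values that were not collected.
- **The illustration may overstate the loss.** Poorly adherent active subjects may not remit at 40%, and the planned rates can be read as already net of withdrawals.
- **Section 3.13 is broader than adherence.** It covers consent-process violations and ineligible enrolment, where agreement on continuation has its own purpose. A blanket change there would go too far.

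SAP 8.1.1 also describes early withdrawal under a treatment-policy strategy and then scores it as failure. That needs reconciling separately; this point does not depend on it.

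**Conclusion.** The point holds in limited form. Sections 3.12 and 3.8.3.1 allow removal from the trial on adherence grounds without a criterion, and do not fit the follow-up policy in 3.8.3.4 and 3.8.3.5. The result is avoidable failure-scored outcomes or, for very early removals, exclusion from the FAS. The expected consequence is dilution: roughly 3 points of power at 5% removal per arm and 7 points at 10%, with type I error essentially unchanged. A biased comparison follows only if removal or nonadherence differs by arm, and nothing in the documents shows that it would. The sizes rest on assumed removal rates and on removed subjects remitting at the planned rates. This should be corrected because the correction is cheap, not because the primary analysis fails without it. SAP section 11 reports early termination with three randomized subjects and no planned analyses performed, so the comment concerns the plan as written.

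**What to change.** Reconcile 3.12 and 3.8.3.1 with 3.8.3.4 and 3.8.3.5. State that nonadherence or a treatment interruption does not by itself end trial participation. The subject is followed for all scheduled assessments, including Week 12, unless consent is withdrawn, the subject is lost to follow-up, or an existing safety or medical provision applies. Decisions about IMP stay where the protocol now places them.

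Leave 3.13 unchanged for consent-process and eligibility violations. Apply the same follow-up default there only to dosing or adherence deviations.

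The cost is a sentence or two in each section. The downside is that the Week 12 visit and ileocolonoscopy, both already scheduled, take place in a few poorly adherent subjects who might otherwise have been dropped.

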3.13 Protocol Deviations

In the event of a significant deviation from the protocol due to an emergency, accident, or mistake (eg, violation of informed consent process, IMP dispensing or subject dosing error, treatment assignment error, subject enrolled in violation of eligibility criteria or concomitant medication criteria), the investigator or designee will contact the sponsor at the earliest possible time by telephone. The investigator and sponsor will discuss the details of the deviation and agree upon the subject's continuation in the trial. This decision will be documented by the investigator and the sponsor, and reviewed by the site monitor.

4 Restrictions

4.1 Prohibited Medications

In vitro studies have shown that OPS-2071 is a substrate of breast cancer resistance protein (BCRP) transporters, UGT1A1 mainly and UGT1A9 partially. Hence, it is recommended to avoid concomitant use of BCRP inhibitors (eg, Estrone, 17 β -estradiol, flavonoids, herb extracts, gefitinib, imatinib, tamoxifen, novobiocin, nelfinavir, ritonavir, dipyridamole, fumitremorgin C, Ko143, cyclosporine, curcumin, eltrombopag, omeprazole, ivermectin) and UGT1A1 or UGT1A9 inhibitors (eg, Silybin, diclofenac, mycophenolic acid, efavirenz, regorafenib).

The following medications are prohibited:

- Use of prednisone or prednisolone > 30 mg/day or budesonide > 9 mg/day, or intravenous steroids, within 4 weeks prior to screening. Low-dose steroids may be tapered down during the trial, based on inflammatory biomarkers and the investigator's judgment.
- Antibiotics (eg, metronidazole, rifaximin, tinidazole, ciprofloxacin, clarithromycin) within 15 days prior to screening or for greater than 2 months within the past year. A short course (maximum of 5 days) of antibiotics will be permitted during the trial, as needed, for indications other than Crohn's disease.
- Nonsteroidal anti-inflammatory drugs
- Antithrombotic drugs:
 - Anticoagulants: heparin or warfarin (also called Coumadin), rivaroxaban (Xarelto), apixaban (Eliquis), edoxaban (Lixiana, Savaysa), betrixaban (Bevyxxa), bivalirudin, argatroban, and desirudin
 - Antiplatelet drugs: clopidogrel (Plavix) and aspirin (aspirin use of \leq 325 mg daily are permitted)

Protocol 341-201-00004

- Quinidine, procainamide, disopyramide, encainide, flecainide, sotalol, amiodarone, ibutilide, dronedarone, or propafenone

Subjects who increase dosages of baseline Crohn's disease medications or take a new therapy for Crohn's disease during the trial will be considered as treatment failures (nonresponders) in the efficacy analysis. These subjects are encouraged to stay in the trial for continuous data collection ([Section 3.8.3.2](#)).

4.2 Other Restrictions

Subjects should be recommended to limit the amount of caffeine to no more than 250 mg of caffeine products such as coffee, tea, soda, energy drinks, chocolate, or chocolate milk per day.

The use of over-the-counter probiotic supplements, including over-the-counter Lactobacillus products, is not permitted.

5 Reporting of Adverse Events

5.1 Definitions

An AE is defined as any untoward medical occurrence in a patient or clinical trial subject administered a medicinal product and which does not necessarily have a causal relationship with this treatment. Adverse events would not include information recorded as medical history at screening for preplanned procedures for which the underlying condition was known and no worsening occurred. Adverse events will be recorded from the time the ICF is signed. Any significant changes from screening should be documented as an AE.

An adverse reaction is any untoward and unintended response to an IMP related to any dose administered. A suspected adverse reaction is any AE for which there is a reasonable possibility that the IMP caused the AE. For the purpose of investigational new drug (IND) safety reporting, "reasonable possibility" means there is evidence to suggest a causal relationship between the IMP and the AE. A suspected adverse reaction implies a lesser degree of certainty about causality.

Protocol 341-201-00004

An SAE includes any event that results in any of the following outcomes:

- Death
- Life-threatening; ie, the subject was, in the opinion of the investigator, at immediate risk of death from the event as it occurred. It does not include an event that, had it occurred in a more severe form, might have caused death.
- Persistent or significant incapacity/disability or substantial disruption of the ability to conduct normal life functions.
- Requires in-patient hospitalization or prolongs hospitalization.
 - Hospitalization itself should not be reported as an SAE; whenever possible the reason for the hospitalization should be reported.
 - Hospitalizations or prolonged hospitalizations for social admissions (ie, those required for reasons of convenience or other nonmedical need) are not considered SAEs.
- Congenital anomaly/birth defect.
- Other medically significant events that, based upon appropriate medical judgment, may jeopardize the subject and may require medical or surgical intervention to prevent one of the outcomes listed above; eg, allergic bronchospasm requiring intensive treatment in an emergency room or home, blood dyscrasias or convulsions that do not result in hospitalization, or the development of drug dependency or drug abuse.

Nonserious adverse events are all AEs that do not meet the criteria for a "serious" AE.

Immediately Reportable Event (IRE):

- Any SAE.
- Any AE related to occupational exposure.
- Potential serious hepatotoxicity (see [Section 5.4](#)).
- Pregnancies are also defined as IREs. Although normal pregnancy is not an AE, it will mandate IMP discontinuation and must be reported on an IRE form to the sponsor. Pregnancy will only be documented on the AE screen in eSource if there is an abnormality or complication.

Adverse events that are stopping rules to be reported directly to the medical monitor are listed in [Section 3.8.3.3](#).

Clinical Laboratory Test Value Changes: It is the investigator's responsibility to review the results of all laboratory tests as they become available. This review will be documented by the investigator's dated signature on the laboratory report. For each abnormal laboratory test result, the investigator needs to ascertain if this is an abnormal (ie, clinically significant) change from baseline for that individual subject. This

Protocol 341-201-00004

determination, however, does not necessarily need to be made the first time an abnormal value is observed. The investigator may repeat the laboratory test or request additional tests to verify the results of the original laboratory tests. If this laboratory value is considered medically relevant by the investigator (subject is symptomatic, requiring corrective treatment or further evaluation), or if the laboratory value leads to discontinuation, and/or fulfills a seriousness criterion, this is considered an AE.

Severity: Adverse events will be graded on a 3-point scale and reported as indicated in eSource. The intensity of an adverse experience is defined as follows:

- 1 = Mild:** Discomfort noticed, but no disruption to daily activity.
- 2 = Moderate:** Discomfort sufficient to reduce or affect normal daily activity.
- 3 = Severe:** Inability to work or perform normal daily activity.

IMP Causality: Assessment of causal relationship of an AE to the use of the IMP is defined as follows:

- Related*:** There is a reasonable possibility of a temporal and causal relationship between the IMP and the AE.
- Not Related:** There is no temporal or causal relationship between the IMP and the AE.

*Investigators should carefully consider consequences of the bowel preparation when assigning causality of AEs (eg, diarrhea).

